8.3.5.2. Exposure During Breastfeeding

An exposure during breastfeeding occurs if:

• A female is found to be breastfeeding while being exposed or having been exposed to study intervention (ie, environmental exposure). An example of environmental exposure during breastfeeding is a female family member or healthcare provider who reports that she is breastfeeding after having been exposed to the study intervention by inhalation or skin contact.

The investigator must report exposure during breastfeeding to Pfizer Safety within 24 hours of the investigator's awareness, irrespective of whether an SAE has occurred. The information must be reported using the CT SAE Report Form. When exposure during breastfeeding occurs in the setting of environmental exposure, the exposure information does not pertain to the participant enrolled in the study, so the information is not recorded on a CRF. However, a copy of the completed CT SAE Report Form is maintained in the investigator site file.

An exposure during breastfeeding report is not created when a Pfizer drug specifically approved for use in breastfeeding women (eg, vitamins) is administered in accord with authorized use. However, if the infant experiences an SAE associated with such a drug, the SAE is reported together with the exposure during breastfeeding.

8.3.5.3. Occupational Exposure

An occupational exposure occurs when a person receives unplanned direct contact with the study intervention, which may or may not lead to the occurrence of an AE. Such persons may include healthcare providers, family members, and other roles that are involved in the trial participant's care.

The investigator must report occupational exposure to Pfizer Safety within 24 hours of the investigator's awareness regardless of whether there is an associated SAE. The information must be reported using the CT SAE Report Form. Since the information does not pertain to a participant enrolled in the study, the information is not recorded on a CRF; however, a copy of the completed CT SAE Report Form is maintained in the investigator site file.

8.3.6. Cardiovascular and Death Events

Not applicable.

8.3.7. Disease-Related Events and/or Disease-Related Outcomes Not Qualifying as AEs or SAEs

Not applicable.

8.3.8. Adverse Events of Special Interest

Not applicable.

8.3.8.1. Lack of Efficacy

This section is not applicable because efficacy is not expected in the study population.

8.3.9. Medical Device Deficiencies

Not applicable.

8.3.10. Medication Errors

Medication errors may result from the administration or consumption of the study intervention by the wrong participant, or at the wrong time, at the wrong dosage strength, or inadvert exposure.

Exposures to the study intervention under study may occur in clinical trial settings, such as medication errors.

Safety Event	Recorded on the CRF	Reported on the CT SAE Report Form to Pfizer Safety Within 24 Hours of Awareness
Medication errors	All (regardless of whether associated with an AE)	Only if associated with an SAE

Medication errors include:

- Medication errors involving participant exposure to the study intervention;
- Potential medication errors or uses outside of what is foreseen in the protocol that do or do not involve the study participant.

Such medication errors occurring to a study participant are to be captured on the medication error page of the CRF, which is a specific version of the AE page.

In the event of a medication dosing error, the sponsor should be notified within 24 hours.

Whether or not the medication error is accompanied by an AE, as determined by the investigator, the medication error is recorded on the medication error page of the CRF and, if applicable, any associated AE(s), serious and nonserious, are recorded on the AE page of the CRF.

Medication errors should be reported to Pfizer Safety within 24 hours on a CT SAE Report Form **only when associated with an SAE**.

8.4. Treatment of Overdose

The sponsor does not recommend specific treatment for an overdose.

In the event of an overdose, the investigator should:

- 1. Contact the medical monitor within 24 hours.
- 2. Closely monitor the participant for any AEs/SAEs and laboratory abnormalities for at least 5 half-lives or 28 calendar days after the overdose of PF-07258669 (whichever is longer).
- 3. Document the quantity of the excess dose as well as the duration of the overdose in the CRF.
- 4. Overdose is reportable to Safety only when associated with an SAE.
- 5. Obtain a blood sample for PK analysis within 5 days from the date of the last dose of study intervention if requested by the medical monitor (determined on a case-by-case basis).

Decisions regarding dose interruptions or modifications will be made by the investigator in consultation with the medical monitor based on the clinical evaluation of the participant.

PFIZER CONFIDENTIAL

Page 53

PFIZER CONFIDENTIAL

Final Protocol Amendment 1, 09 November 2020	
CCI	
CCI	
CCI	
CCI	
CCI	
CCI	

PF-07258669 Protocol C4541001

CCI	
CCI	
CCI	
CCI	

8.7. Genetics

8.7.1. Specified Genetics

Genetics (specified analyses) are not evaluated in this study.

8.7.2. Banked Biospecimens for Genetics

A 2-mL blood sample optimized for DNA isolation Prep D1.5 will be collected as local regulations and IRBs/ECs allow.

Banked Biospecimens may be used for research related to the study intervention(s). Genes and other analytes (eg, proteins, RNA, nondrug metabolites) may be studied using the banked samples.

PFIZER CONFIDENTIAL

See Appendix 5 for information regarding genetic research. Details on processes for collection and shipment of these samples can be found in the lab manual and other supporting documentation.

CCI	
CCI	
CCI	
CCI	
CCI	
CCI	
DELZED CONFU	

8.8.2. Banked Biospecimens for Biomarkers

Additional Banked Biospecimens in this study are:

• 10-mL whole blood (Prep B2 optimized for serum).

Banked Biospecimens will be collected as local regulations and IRB/ECs allow. Banked Biospecimens may be used for research related to the study intervention(s) and safety biomarkers. Genes and other analytes (eg, proteins, RNA, nondrug metabolites) may be studied using the banked samples. See Appendix 5 for information regarding genetic research. Details on processes for collection and shipment of these samples can be found in the lab manual and other supporting documentation.

8.8.3. Specified Gene Expression (RNA) Research

Specified gene expression (RNA) research is not included in this study.

8.8.4. Specified Protein Research

Specified protein research is not included in this study.

8.8.5. Specified Metabolomic Research

Specified metabolomic research is not included in this study.

8.9. Immunogenicity Assessments

Immunogenicity assessments are not included in this study.

8.10. Health Economics

Health economics/medical resource utilization and health economics parameters are not evaluated in this study.

9. STATISTICAL CONSIDERATIONS

Detailed methodology for summary and statistical analyses of the data collected in this study is outlined here and further detailed in a SAP, which will be maintained by the sponsor. The SAP may modify what is outlined in the protocol where appropriate; however, any major modifications of the primary endpoint definitions or their analyses will also be reflected in a protocol amendment.

9.1. Statistical Hypotheses

No formal hypothesis tests are planned for this study.

9.2. Sample Size Determination

A sample size of up to approximately 8 participants per cohort (approximately 6 participants receiving PF-07258669 and up to 2 participants receiving placebo within each period) has been chosen based on the need to minimize first exposure to humans of a new chemical entity and the requirement to provide adequate safety, tolerability, and PK assessment at each dose level. There are 2 planned cohorts and an additional optional third cohort which will only be used if the objectives of the study are not fulfilled in Cohort 1 and Cohort 2.

Participants who discontinue prior to completion of the study may be replaced, at the discretion of the investigator and sponsor.

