1.2. Schema

- Screening to dosing on Day 1 in Period 1: Maximum of 28 days for each cohort.
- Inpatient stay in each period: Day -1 to minimum of Day 3 (ie, 48 hours post-dose).
- In each period, 6 participants will be randomized to receive PF-07258669, and 2 participants will receive matching-placebo.
- Precautionary sentinel dosing will be used in each period of each cohort. Two participants (1 receiving PF-07258669 and 1 receiving placebo) within a period will be dosed initially before the remaining participants of that period are dosed. Safety and tolerability data through at least 24 hours post-dose for the sentinel participants will be reviewed prior to dosing the remaining participants of that period.
- The starting dose level in Period 1 of Cohort 1 is 0.1 mg. All other planned dose levels in other periods and cohorts may be adjusted pending emerging safety, tolerability, and PK data from previous periods and cohorts.
- On-site follow-up visit to occur on Day 8 ±2 days in Period 4 only, with an additional follow-up contact occurring 28-35 days after administration of the final dose of study intervention.

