9.4.1.1. Electrocardiogram Interval Analyses

Changes from baseline for the ECG parameters (ie, QT interval, heart rate, QTcF interval, PR interval, and QRS complex) will be summarized by treatment and time.

The number (%) of participants with maximum postdose QTcF values and maximum increases from baseline in the following categories will be tabulated by treatment:

Degree of Prolongation	Mild (msec)	Moderate (msec)	Severe (msec)
Absolute value	>450-480	>480-500	>500
Increase from baseline		30-60	>60

Safety QTcF Assessment

In addition, the number of participants with uncorrected QT values >500 msec will be summarized.

When more than 1 ECG is collected at a nominal time after dose administration (for example, triplicate ECGs), the mean of the replicate measurements will be used to represent a single observation at that time point. If any of the 3 individual ECG tracings has a QTcF value >500 msec, but the mean of the triplicates is not >500 msec, the data from the participant's individual tracing will be described in a safety section of the CSR in order to place the >500-msec value in appropriate clinical context. However, values from individual tracings within triplicate measurements that are >500 msec will not be included in the categorical analysis unless the average from the triplicate measurements is also >500 msec. Changes

from baseline will be defined as the change between the postdose QTcF value and the average of the predose triplicate values on Day 1.

In addition, an attempt may be made to explore and characterize the relationship between plasma concentration and QT interval length using a PK/PD modeling approach. If a PK/PD relationship is found, the impact of participant factors (covariates) on the relationship may be examined. The results of such analyses will not be included in the CSR.

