### 5.2. General Methods

Unless specified otherwise, summaries will be produced by treatment.

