## **6. ANALYSES AND SUMMARIES**

### **6.1. Primary Endpoint(s)**

#### **6.1.1. Adverse Events**

Adverse events will be listed and summarized by treatment, in accordance with sponsor reporting standards using the safety population defined in Section 4.

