#### **6.1.3. Vital Signs**

Absolute values and changes from baseline in supine, standing and postural changes for systolic and diastolic BP and pulse rate will be listed and summarized by treatment and timepoint,

according to sponsor reporting standards, using the safety population defined in Section 4. Tables will be paged by parameter. Baseline is as defined in Section 3.1.3.

Mean changes from baseline for supine, standing and postural changes for systolic and diastolic BP and pulse rate will be plotted against time post-dose. On each plot there will be one line for each treatment. Data from all cohorts will be plotted on the same figure using a single line for the pooled placebo. Corresponding individual plots of changes from baseline will also be produced for each treatment.

Maximum decrease from baseline for supine and standing systolic and diastolic BP, maximum increase from baseline for standing and supine pulse rate, and maximum increase from baseline for postural differences (in systolic and diastolic BP, and pulse rate) will be summarized by treatment, according to sponsor reporting standards.

Maximum/minimum absolute values and changes from baseline for vital signs (for supine, standing and postural) will also be summarized descriptively by treatment using categories as defined in [Appendix 2](#). Numbers and percentages of participants meeting the categorical criteria will be provided. All planned and unplanned post-dose timepoints will be counted in these categorical summaries. All values meeting the criteria of potential clinical concern will be listed.

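### Dose is largely aliased with period within a cohort, and no visible safety output shows placebo by period; adverse-event incidence is most exposed because Period 4 has a longer collection window

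*Protocol*

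**What the plan says.** Protocol 1.2 sets the allocation: "In each period, 6 participants will be randomized to receive PF-07258669, and 2 participants will receive matching-placebo". Protocol 9.2 words it as "approximately 6 participants receiving PF-07258669 and up to 2 participants receiving placebo within each period". Protocol 4.1 gives each participant four periods, with three active doses and one placebo dose. Doses ascend after review of the prior level, but Protocol 4.2, 4.3.3 and 6.6 allow levels to be repeated or changed.

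The default for outputs is in SAP 5.2: "Unless specified otherwise, summaries will be produced by treatment". SAP 6.1.1 says "Adverse events will be listed and summarized by treatment", and 6.1.2 does the same for laboratory data. Protocol 9.4.1.1 says ECG changes "will be summarized by treatment and time". For the mean-change plots of vital signs, SAP 6.1.3 says "Data from all cohorts will be plotted on the same figure using a single line for the pooled placebo"; 6.1.5, 6.1.6 and 6.1.7 repeat this for ECG, respiratory rate and oral temperature. No visible summary or model has a period factor.

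Baseline is taken before dosing in every period (SAP 3.1.2, 3.1.3, 3.1.5 to 3.1.7). SAP 3.1.1 attributes events in washout or follow-up to the most recent dose, up to the contact 28 to 35 days after the last dose. Protocol 1.3 sets a washout of at least 7 days and places the on-site Day 8 visit in Period 4 only. SAP 6.1.3 counts all planned and unplanned post-dose timepoints in the vital-sign categories.

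**The concern.** A new dose level normally occupies one period of one cohort, so within a cohort the comparison of doses is also a comparison of periods. The placebo participants randomised in the same period are what separates the two. Protocol 4.2 itself ties blinded placebo in each period to an unbiased safety assessment. Once placebo is pooled over periods, that separation is lost: a Period 4 dose is compared with placebo data that come mostly from Periods 1 to 3.

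The description of safety by dose is the whole analysis of the primary objective. If periods differ for reasons other than dose, a pooled comparison can show a dose pattern that is not there, or flatten one that is. For adverse events the periods differ by plan, because the length of observation is not the same.

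**Working it through.** **Design figures.** 3 cohorts × 8 = 24, the stated maximum. Per period, 8 × 3/4 = 6 active and 8 × 1/4 = 2 placebo, as stated. Pooled placebo is 16 values with two cohorts and 24 with three. Each period contributes a quarter, so 3/4 come from Periods 1 to 3. The plan states no power or precision figure.

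**General form of the error.** With no drug effect and an assumed linear drift d per period, dose minus pooled placebo in period k is d × (k − 2.5), that is −1.5d, −0.5d, +0.5d and +1.5d. The false change from the first to the last dose of a cohort is 3d. The documents give no value of d. This applies to absolute values, and to post-dose changes only if the post-dose course itself drifts. A drift in pre-dose level cancels in change from baseline.

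**Adverse-event window (from the plan's own rules).**

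- Period 4 window: 28 to 35 days (SAP 3.1.1).
- Periods 1 to 3 window: from dose to next dose, at least 7 days (Protocol 1.3). Protocol 4.1 gives about 14 weeks of participation, or 98 days. If that includes 28 days of screening and 28 to 35 days of follow-up, the three intervals average (98 − 28 − 28)/3 = 14 days to (98 − 28 − 35)/3 = 11.7 days.
- Assumption: constant background hazard of 1% per day and no drug effect. The probability of any event in t days is 1 − exp(−0.01t).

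With 14 days in Periods 1 to 3 and 28 days in Period 4:

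- Periods 1 to 3: 1 − exp(−0.14) = 13.1%
- Period 4: 1 − exp(−0.28) = 24.4%
- Pooled placebo: (3 × 13.1 + 24.4)/4 = 15.9%
- Period 4 dose minus pooled placebo: +8.5 points

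With 7 and 35 days:

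- Periods 1 to 3: 6.8%; Period 4: 29.5%
- Pooled placebo: (3 × 6.8 + 29.5)/4 = 12.5% (12.45% unrounded)
- Period 4 dose minus pooled placebo: +17 points

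Same-period placebo has the same window as the dose, so its expected difference is zero. Separately, the Day 8 visit gives Period 4 an extra chance to meet a vital-sign category.

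**Would same-period placebo be the better comparator?** Assumed inputs for absolute supine systolic pressure: two cohorts, between-participant SD 10, residual SD 6, drift −2 mm Hg per period. For a Period 4 dose (6 active):

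- Same-period placebo, 4 values over two cohorts: variance 136 × (1/6 + 1/4) = 56.7, SE 7.5, bias 0, RMSE 7.5.
- Pooled placebo, 16 values, which include the same six participants: variance 100 × [6 × (1/6 − 1/16)² + 10 × (1/16)²] + 36 × (1/6 + 1/16) = 10.4 + 8.25 = 18.7, SE 4.3. Bias is −2 × 1.5 = −3.0, so RMSE = √(18.7 + 9) = 5.3.
- Mixed model with participant random and period fixed, common to both cohorts: bias 0, RMSE 4.6 (generalised least squares on the planned layout).

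Pooled placebo beats raw same-period placebo here despite its bias. A participant-plus-period model does better than either.

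**The case against.** The strongest case against the point has four parts.

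- A reader might infer that any period drift contaminates all the safety outputs. The documents do not support that. Pooling is written out only for four sets of mean-change plots, and the per-period baseline removes level drift from exactly those. For adverse-event and laboratory tables, pooling is the plain reading of a by-treatment summary, but the sponsor reporting standards are not visible. Laboratory assessment also takes the baseline result into account (SAP 3.1.2), and the vital-sign categories include change criteria.
- A reader might infer a false dose response over the whole dose range. The dose table and schema are not visible, and levels may be repeated or lowered. If the second cohort continues above the first, the error is a sawtooth with an overall slope of about 0.24d per dose step, not 1.0d as within a cohort.
- A reader might conclude that each dose should be read first against same-period placebo. Under the assumed inputs above, that raises total error. With four placebo participants, one event moves the rate by 25 points, and at a 20% background rate no event is seen 0.8⁴ = 41% of the time.
- Nothing is tested: Protocol 9.1 says "No formal hypothesis tests are planned for this study". Escalation is decided level by level, with at least one placebo participant completing the prior level (Protocol 6.6) and with unblinded sponsor review permitted (Protocol 9.5). The pooled outputs come after database lock.

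All four stand as limits on the point. None answers the unequal adverse-event window or the extra Period 4 visit, which come from the plan's own rules and which a period-specific baseline does not correct.

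**Conclusion.** The point holds in limited form. Within a cohort, dose is broadly aliased with period, and no visible output shows the placebo randomised in the same period. What is exposed is adverse-event incidence, absolute and categorical laboratory, vital-sign and ECG outputs, and any post-dose course that differs by period.

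The firmest part is the adverse-event window. With no drug effect and an assumed 1% per day background, a Period 4 dose would show an excess of about 8.5 points (14- and 28-day windows) to 17 points (7 and 35 days) over pooled placebo. The direction follows from SAP 3.1.1; the size depends on the assumed rate and on the actual washout. Sizes for other kinds of drift rest wholly on assumed values.

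The sample-size paragraph contains no error: its stated basis is that the number "has been chosen based on the need to minimize first exposure to humans of a new chemical entity". The consequence is for interpretation only, and the grade is CONSIDER.

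**What to change.** In SAP 5.2 and 6.1.1 to 6.1.7:

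- Keep pooled placebo as the main display.
- Add supportive placebo columns for Periods 1, 2, 3 and 4, combined over cohorts, for adverse events and for absolute and categorical laboratory, vital-sign and ECG outputs.
- Present adverse-event incidence also over a post-dose window of equal length in all periods, no longer than the shortest washout used.
- If a supportive model is fitted, include period as a fixed effect and participant as random.
- State in the study report that dose and period are aliased within a cohort.

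Do not make same-period placebo the first comparator.

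The cost is SAP wording and extra table columns, with no new data. The downside is that each added column holds only 4 placebo values with two cohorts, or 6 with three, and will be noisy; it should be labelled supportive.

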9.3. Analysis Sets

Participant Analysis Set	Description
Enrolled/Randomly assigned to study intervention	"Enrolled" means a participant's, or their legally authorized representative's, agreement to participate in a clinical study following completion of the informed consent process. Potential participants who are screened for the purpose of determining eligibility for the study, but do not participate in the study, are not considered enrolled, unless otherwise specified by the protocol.
Evaluable	All participants randomly assigned to study intervention and who receive a dose of study intervention.
Safety	All participants randomly assigned to study intervention and who receive a dose of study intervention. Participants will be analyzed according to the product they actually received.
PK Concentration	All participants randomly assigned to study intervention and who receive a dose of study intervention and in whom at least 1 plasma concentration value is reported.
PK Parameter	All participants randomly assigned to study intervention and who receive a dose of study intervention and have at least 1 of the PK parameters of interest calculated.

For purposes of analysis, the following analysis sets are defined:

9.4. Statistical Analyses

The SAP will be developed and finalized before any analyses are performed and will describe the analyses and procedures for accounting for missing, unused, and spurious data. This section is a summary of the planned statistical analyses of the primary and secondary endpoints. Analysis of the tertiary/exploratory endpoints will be documented in the SAP.

9.4.1. Safety Analyses

All safety analyses will be performed on the safety population.

AEs, ECGs, BP, pulse rate, respiratory rate, oral body temperature, continuous cardiac monitoring, and safety laboratory data will be reviewed and summarized on an ongoing basis during the study to evaluate the safety of participants. Any clinical laboratory, ECG, BP, pulse rate, and respiratory rate abnormalities of potential clinical concern will be described. Safety data will be presented in tabular and/or graphical format and summarized descriptively, where appropriate.

Medical history, physical examination, and neurological examination information, as applicable, collected during the course of the study will be considered source data and will not be required to be reported, unless otherwise noted. However, any untoward findings identified on physical and/or neurological examinations conducted during the active collection period will be captured as AEs, if those findings meet the definition of an AE. Data collected at screening that are used for inclusion/exclusion criteria, such as laboratory data, ECGs, and vital signs, will be considered source data, and will not be required to be reported, unless otherwise noted. Demographic data collected at screening will be reported. In addition, selected screening laboratory data may be reported.

